#### **Analysis methods**

No missing data imputation will be performed. The proportion of patients with 6-month disability improvement at the end of study will be presented including associated 95% Clopper Pearson exact intervals. Disability improvement at Visit 2 and Visit 3 will also be presented and derived in the same way as described for Visit 4.

# 14.4.2 Sensitivity Analyses of the Secondary Outcome 6-month Disability Improvement

Four sensitivity analyses will be performed to assess the robustness of the results of the secondary outcome 6-month disability improvement.

The first sensitivity analysis will be a complete case analysis that will derive disability improvement only for cases where it can be determined without reservations, setting all the other cases to missing. This means that if only one or two out of the three assessments are available, disability improvement will either be "Yes" if those are sufficient for the assessment or "Missing" if improvement criteria are not observed in any of the available assessments. The number of patients included in these analyses will be less than the ones includes in the main analysis.

The second sensitivity analysis will include an NR missing data imputation. All patients for which disability improvement cannot be assessed or is "No" but not all three assessments are available will be set to "No".

In this case, it is expected that the complete cases approach will overestimate the true treatment effect while the NR will provide an underestimation of the true treatment effect.

A third sensitivity analysis will be performed using EDSS only for disability assessment derivation.

The fourth sensitivity analysis will replicate the above described third sensitivity analysis but by two subgroups:

- Patients with at least one EDSS score obtained within 3 months following a relapse
- Patients with both EDSS scores obtained more than 3 months following a relapse

## 14.4.3 Subgroup Analyses of the Secondary Outcome 6-month Disability Improvement

The subgroup analyses will be performed on the secondary outcome assessment based on the FAS for all subgroup levels defined in IAP Section 8.2 "Subgroup definition and parametrization". All the subgroup analyses are exploratory and will be performed unstratified.

A bar plot with disability improvement from Visit 1 to Visit 4 overall and by subgroup will be presented.

## 15 Safety Analyses

Safety analyses will be done on the FAS.

#### 15.1 Adverse Events

The TEAE are those events with onset dates occurring within the on-treatment periods as defined in Section 9.7.

The AEs related to study treatment are those events with relationship missing or "Related".

All analyses described in Section 15.1 will be based on TEAEs if not otherwise specified. The AE listings will include all AEs (whether treatment-emergent or not). AEs outside the on-treatment period will be flagged in the listings.

Unless otherwise specified, TEAEs will be summarized by number and percentage of patients with the TEAE in the category of interest, primary SOC and PT in decreasing frequency.

Each participant will be counted only once within each SOC or PT. If a participant experiences more than one AE within a SOC or PT for the same summary period, only the AE with the strongest relationship or the worst severity, as appropriate, will be included in the summaries of relationship and severity.

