- 1) Life-threatening in this context refers to a reaction in which the patient was at risk of death at the time of the reaction; it does not refer to a reaction that hypothetically might have caused death if more severe.
- 2) Medical and scientific judgement should be exercised in deciding whether other situations should be considered as serious reactions, such as important medical events that might not be immediately life threatening or result in death or hospitalization but might jeopardise the patient or might require an intervention to prevent one of the other outcomes listed above. Such important medical events should be considered as serious.

Examples of such events are intensive treatment in an emergency room or at home for allergic bronchospasm, blood dyscrasias or convulsions that do not result in hospitalization or development of dependency or abuse. As a guidance, the important medical event (IME) terms list is intended to be used for assessment of suspected adverse reactions (see EMA/207865/2017).

Any suspected transmission via a medicinal product of an infectious agent is also considered a serious adverse reaction.

Adverse Events of Special Interest (AESI)

An AESI is an AE of scientific and medical concern specific to the sponsor's product or program, for which ongoing monitoring and rapid communication by the Investigator to the sponsor can be

appropriate. AESIs for monitoring should then be collected following the procedure for an SAE described in Section 11.4.

The study-specific data will be registered for each of the following events and the known related risk factors:

For complete and accurate information, the data collected on these pre-defined events will include as much detail as possible to corroborate diagnosis, including but not limited to histopathologic results, and relevant laboratory and imaging results.

Malignancy: Any occurrence of malignant neoplasms during the study period. These will be classified overall and by type. Malignancies will include all physician-diagnosed and pathologically confirmed solid tumours (including non-melanoma skin cancer) and lymphoproliferative/haematopoietic neoplastic diseases. Benign tumours will not be collected.

Severe and/or serious infections: The above mentioned 4 categories will follow as: Any occurrence during the study period, regardless of the causative agent and the duration of infection, will be recorded. All of the following will be considered:

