- · Bacterial, viral, fungal, parasitic and protozoal infections
- Severe and/or serious infections will be defined by their management or their outcome: all
 infections that result in death or hospitalisation or require the use of intravenous treatment
 (e.g. antibiotics)
- Opportunistic infections are defined as an invasive infection caused by microorganisms that
 are normally non-pathogenic or rarely pathogenic in individuals with normal immune
 function or cause an infection of a type or severity not seen in the normal host; opportunistic
 infections exclude herpetic infection
- Herpes zoster (not considered an opportunistic infection). Only severe and/or serious herpes zoster will be collected.

The duration of infections will be the difference between start date and recovery date as reported by the treating physician.

Patients may contribute more than I episode to this analysis if, after resolution as defined, another infection occurs.

Severe lymphopenia: Any occurrence of severe (or worse) lymphopenia during the study period, classified as Grade ≥ 3. As per the Common Terminology Criteria for Adverse Events (CTCAE) (v4.03: June 14, 2010) from the National Institutes of Health, the grades of lymphopenia are defined based on laboratory test results that indicate a decrease in number of lymphocytes in a blood sample:

- Grade 3 (severe lymphopenia): <500 200/mm³; <0.5 0.2 x10⁹ /L
- Grade 4 (serious lymphopenia): <200/mm³; <0.2 x 10⁹ /L

Duration of severe lymphopenia: It is defined as the interval from the finding of severe lymphopenia until resolution, which is the achievement of a CTCAE Grade I [ranging from the

lower limit of normal (LLN) to 800/mm³] or normalization (above LLN i.e. normal lymphocyte count or CTCAE Grade 0). Patients may contribute more than 1 episode to this analysis if, after resolution as defined, severe lymphopenia occurs again. The frequency of lymphocyte counts in patients with severe lymphopenia will be described with special emphasis on the number and timing of lymphocyte counts in relation to Cladribine tablets dosing and during episodes of severe lymphopenia.

Events not to be considered as Adverse Events

Medical conditions present at study start, that do not worsen in severity or frequency during the study are defined as Baseline Medical Conditions and are NOT to be considered AEs.

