## 7 Changes to the Planned Analyses in the Clinical Study Protocol

There are no changes to the analyses planned per protocol.

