#### 15.1.1 All Adverse Events

The AEs will be summarized using the latest version of MedDRA PT as event category and MedDRA primary SOC body term as body system category.

Incomplete AE-related dates will be handled as specified in Section 9.8.1.

The following tables will be created

- TEAE summary table with the number and percentage of patients having:
  - o TEAE
  - TEAE of Special Interest (TEAESI)
  - TEAE leading to death
  - o TEAE leading to Cladribine dose reduction
  - o TEAE leading to Cladribine temporary discontinuation
  - o TEAE leading to Cladribine permanent discontinuation
  - TEAE leading to study termination
  - TEAE not recovered/resolved
  - Any serious TEAE:
    - TEAESI
    - Leading to death
    - Leading to Cladribine dose reduction

- Leading to Cladribine temporary discontinuation
- Leading to Cladribine permanent discontinuation
- Leading to study termination
- Not recovered/resolved
- Cladribine related TEAE:
  - TEAESI
  - Serious
  - Leading to death
  - Leading to Cladribine dose reduction
  - Leading to Cladribine temporary discontinuation
  - Leading to Cladribine permanent discontinuation
  - Leading to study termination
  - Not recovered/resolved
- Incidence of TEAE by Primary SOC and PT
- Incidence of Serious TEAE by Primary SOC and PT
- Incidence of Serious TEAE related to Cladribine by Primary SOC and PT
- Incidence of TEAE leading to Cladribine temporary discontinuation Primary SOC and PT
- Incidence of related TEAE leading to Cladribine temporary discontinuation Primary SOC and PT
- Incidence of TEAE leading to Cladribine permanent discontinuation Primary SOC and PT
- Incidence of related TEAE leading to Cladribine permanent discontinuation Primary SOC and PT
- Incidence of TEAE leading to death by Primary SOC and PT
- Incidence of related TEAE leading to death by Primary SOC and PT
- Incidence of TEAE by Primary SOC and PT and relationship to Cladribine
- Incidence of TEAE by Primary SOC and PT and severity
- Incidence of TEAESI by Primary SOC and PT and severity
- Incidence of TEAESI by Primary SOC and PT and by relationship to Cladribine

2.0

• Incidence of Serious TEAESI by Primary SOC and PT and by relationship to Cladribine

All AEs regardless of being treatment-emergent or not will be listed.

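### Protocol 11.1 describes an episode-based analysis of adverse events of special interest, but the SAP summarises them only as patients counted once per SOC or PT

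*SAP*

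**What the plan says.** Protocol 11.1 names three groups of adverse events of special interest.

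- **Malignancy.** "These will be classified overall and by type"
- **Severe and/or serious infections.** "Severe and/or serious infections will be defined by their management or their outcome: all" those leading to death, hospital admission or intravenous treatment. Opportunistic infection has its own definition, based on invasiveness, organism and host immune function, and excludes herpetic infection. Herpes zoster is separate, and only severe or serious cases are collected. On duration: "The duration of infections will be the difference between start date and recovery date as reported by the treating physician". On repeats: "Patients may contribute more than I episode to this analysis if, after resolution as defined, another infection occurs".
- **Severe lymphopenia (Grade 3 or higher).** Duration runs from the finding until recovery to Grade 1 or normal. On repeats: "Patients may contribute more than 1 episode to this analysis if, after resolution as defined, severe lymphopenia occurs again".

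SAP 15.1 summarises treatment-emergent events as numbers and percentages of patients unless otherwise specified, and adds: "Each participant will be counted only once within each SOC or PT". SAP 15.1.1 has TEAESI lines in the overview table and three TEAESI tables, of which the first is "Incidence of TEAESI by Primary SOC and PT and severity". The other two split all TEAESIs, and serious TEAESIs, by relationship to treatment. SAP 7 states: "There are no changes to the analyses planned per protocol".

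**The concern.** The protocol's episode rules refer to an analysis, and the SAP contains no such analysis. No exception to the once-per-patient rule is made for events of special interest. The SAP lists no episode count, no episode duration and no row for opportunistic infection.

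Safety at two years is a stated secondary objective, and these are the events the protocol singled out. Under the SAP as written, the report's tables would not say how many infection or severe lymphopenia episodes occurred, how long they lasted, or how many patients had an opportunistic infection. Anyone who wanted those figures would have to classify and count from listings after seeing the data, with no rule fixed in advance.

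**Working it through.** The documents state no AESI rate and no precision target for safety, so there is no figure to reproduce. The check is a comparison of texts, followed by an illustration of size.

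**Comparison**

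| Element in Protocol 11.1 | Where it appears in the SAP |
|---|---|
| More than one infection episode per patient | No episode count; a repeat under the same PT adds nothing to the tables |
| More than one severe lymphopenia episode per patient | Same |
| Infection duration, start to recovery | No summary |
| Severe lymphopenia duration, finding to resolution | No summary |
| Opportunistic infection | No row among on-study events; SAP 11.2 does use a severe opportunistic infection category for medical history |
| Severe/serious infection | No row by that name; approximated by infection rows of the TEAESI tables |
| Severe/serious herpes zoster | No row by that name; largely recoverable from PT rows |
| Malignancy overall and by type | No row by that name; largely recoverable from SOC and PT rows |

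The TEAESI table planned for the interim analyses (SAP 18.2) is also by SOC and PT.

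The splits by severity and seriousness do not supply the missing categories. Severity in Protocol 11.2 is graded by effect on the patient's functioning, whereas the infection category rests on management or outcome. An infection that qualifies only because intravenous treatment was used need not meet a seriousness criterion. PT rows cannot be added up to patients either, since one patient can appear under several PTs.

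**Illustration of size (rates assumed, not from the documents)**

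Inputs: N = 242 (Protocol 9.5); λ = mean episodes per patient over two years, assumed 0.02 to 0.20.

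- Expected episodes: N × λ.
- Patients with at least one episode, independent episodes (Poisson): N × (1 − e^(−λ)).
- Patients with at least one episode, strong clustering (negative binomial, shape k = 0.2, assumed): N × (1 − (k/(k+λ))^k).
- Share of episodes hidden by counting patients once: 1 − patients/episodes.

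| λ | Episodes | Patients, independent | Hidden | Patients, clustered | Hidden |
|---|---|---|---|---|---|
| 0.02 | 4.84 | 4.79 | 1.0% | 4.57 | 5.6% |
| 0.05 | 12.10 | 11.80 | 2.5% | 10.56 | 12.7% |
| 0.10 | 24.20 | 23.03 | 4.8% | 18.85 | 22.1% |
| 0.20 | 48.40 | 43.87 | 9.4% | 31.33 | 35.3% |

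Example, λ = 0.05: 242 × 0.05 = 12.10 episodes; 242 × (1 − e^(−0.05)) = 11.80 patients; 1 − 11.80/12.10 = 2.5%. With clustering, 242 × (1 − (0.2/0.25)^0.2) = 10.56 patients; 1 − 10.56/12.10 = 12.7%.

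These compare all episodes with patients counted once overall. Within a single PT the loss is smaller, because only repeats of that same PT are hidden.

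**The case against.** The strongest defence is that the SAP sets out to implement Protocol 9.7 (see SAP 4), and Protocol 9.7 specifies no AESI statistic. The episode rules sit in the chapter on managing and reporting adverse events and are worded permissively. The protocol endpoint is the occurrence of adverse and serious adverse events, which patient-level incidence answers. This weakens any charge that SAP 7 is plainly false. It does not remove the gap: Protocol 11.1 speaks of an analysis, and Protocol 9.7 leaves detailed methods for the study's data to the SAP.

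A reader might go further than the documents allow in three ways.

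- **That all AESIs are pooled or not shown.** Only the overview lines treat them as one group; the three tables split them by SOC and PT. Every adverse event is listed, and serious events have separate listings with criteria and narratives. A repeat infection with a different PT gets its own PT row.
- **That patients with a severe or serious infection cannot be counted.** Because the infection AESI is itself the severe/serious group and each patient counts once per SOC, the infection SOC row gives roughly that number. Zoster and malignancy type can largely be read from the PT rows. Only opportunistic infection clearly lacks a near equivalent.
- **That a fixed percentage of episodes is lost.** The tables are labelled as patients and present no episode total, and any percentage depends on assumed rates and clustering.

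**Conclusion.** The gap is real and narrow. Protocol 11.1 describes episode counts and durations for infections and severe lymphopenia, and a distinct opportunistic infection category. The SAP provides none of these as a summary and does not declare the omission. The accurate description is that these data are listed but not summarised by episode or by protocol category.

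That conclusion rests on the text alone. The numerical range (about 1% to 9% of episodes hidden if independent, about 6% to 35% with strong clustering) depends wholly on the assumed rates and shape parameter, and shows only that the effect could be anywhere from trivial to material. The change is worth making because it is cheap and delivers what the protocol describes for its two-year safety objective. Nothing here touches the primary analysis or the sample size.

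**What to change.** Keep the SOC/PT tables and add one table to SAP 15.1.1, with these rows:

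- malignancy, overall and by type;
- severe/serious infection, with opportunistic infection and severe/serious herpes zoster as sub-rows;
- lymphopenia of Grade 3 or higher.

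For each row give the number and percentage of patients with at least one event and the number of episodes, counting a new episode only after resolution as Protocol 11.1 defines it. Summarise episode duration for infections and for severe lymphopenia. A rate per patient-year is optional; the protocol does not ask for one. If the sponsor prefers to leave any element to listings, SAP 7 should say so.

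The cost is one table. The documents name an AESI report form but do not show its fields. If the form does not record whether an infection was opportunistic, the infections will have to be classified against the protocol definition before database lock.

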#### 15.1.1 All Adverse Events

The AEs will be summarized using the latest version of MedDRA PT as event category and MedDRA primary SOC body term as body system category.

Incomplete AE-related dates will be handled as specified in Section 9.8.1.

The following tables will be created

- TEAE summary table with the number and percentage of patients having:
  - o TEAE
  - TEAE of Special Interest (TEAESI)
  - TEAE leading to death
  - o TEAE leading to Cladribine dose reduction
  - o TEAE leading to Cladribine temporary discontinuation
  - o TEAE leading to Cladribine permanent discontinuation
  - TEAE leading to study termination
  - TEAE not recovered/resolved
  - Any serious TEAE:
    - TEAESI
    - Leading to death
    - Leading to Cladribine dose reduction

- Leading to Cladribine temporary discontinuation
- Leading to Cladribine permanent discontinuation
- Leading to study termination
- Not recovered/resolved
- Cladribine related TEAE:
  - TEAESI
  - Serious
  - Leading to death
  - Leading to Cladribine dose reduction
  - Leading to Cladribine temporary discontinuation
  - Leading to Cladribine permanent discontinuation
  - Leading to study termination
  - Not recovered/resolved
- Incidence of TEAE by Primary SOC and PT
- Incidence of Serious TEAE by Primary SOC and PT
- Incidence of Serious TEAE related to Cladribine by Primary SOC and PT
- Incidence of TEAE leading to Cladribine temporary discontinuation Primary SOC and PT
- Incidence of related TEAE leading to Cladribine temporary discontinuation Primary SOC and PT
- Incidence of TEAE leading to Cladribine permanent discontinuation Primary SOC and PT
- Incidence of related TEAE leading to Cladribine permanent discontinuation Primary SOC and PT
- Incidence of TEAE leading to death by Primary SOC and PT
- Incidence of related TEAE leading to death by Primary SOC and PT
- Incidence of TEAE by Primary SOC and PT and relationship to Cladribine
- Incidence of TEAE by Primary SOC and PT and severity
- Incidence of TEAESI by Primary SOC and PT and severity
- Incidence of TEAESI by Primary SOC and PT and by relationship to Cladribine

2.0

• Incidence of Serious TEAESI by Primary SOC and PT and by relationship to Cladribine

All AEs regardless of being treatment-emergent or not will be listed.

## 15.1.2 Adverse Events Leading to Discontinuation of Study Treatment

The frequency (number and percentage) of patients with TEAE leading to temporary or permanent Cladribine discontinuation will be presented in the TEAE summary table. Summaries by SOC and PT will also be presented with TEAE and related TEAE that led to temporary and permanent Cladribine discontinuation as described in the previous section.

## 15.2 Deaths, Other Serious Adverse Events, and Other Significant Adverse Events

#### **15.2.1** Deaths

All TEAE that led to death will be presented descriptively as explained in other sections.

A Listing with death details, including date of death, the primary reason of death and autopsy results if available will be created. Additionally, the number of linked serious adverse event (SAE) will be provided. Details on the SAE narrative will be presented in SAE narratives listing.

#### 15.2.2 Serious Adverse Events

The following overall frequency tables will be prepared for SAEs:

- Incidence of serious AEs by SOC and PT
- Incidence of related serious AEs by SOC and PT

Separate Listings including only SAEs will be presented, including SAE criteria met and narratives of SAEs.

### **Analyses of Other Outcomes**

### 16.1 Patient Reported Outcome MSIS29

## 16.1.1 Patient Reported Outcome MSIS29: Derivation and analysis of the Patient Reported Outcome MSIS29

#### **Derivations**

MSIS-29 has two available scores: physical and psychological score. Derivation of both scores from the questionnaire is presented at IAP Section 9.9.1.

#### **Analysis methods**

No missing data imputation will be performed. Summary statistics will be provided for each score independently by visit (Baseline, Visit 2 and Visit 4). For Visit 2 and Visit 4 scores, only measurements collected within the period of  $\pm$  30 days as compared to the predicted schedule will be considered for analysis. Measurements obtained outside this window will be set to missing. For post-baseline visits, absolute and relative change from baseline will be summarized, including 95% CIs for the difference between each visit scores and baseline score.

### 16.2 Patient Reported Outcome TSOM v1.4

## 16.2.1 Patient Reported Outcome TSQM v1.4: Derivation and analysis of the Patient Reported Outcome TSQM v1.4

#### **Derivations**

TSQM v1.4 has four Specific Domains (Global Satisfaction, Effectiveness, Side Effects and Convenience). Details on how to derive these components are presented at IAP Section 9.9.2.

